7.1.3 Medical Adherence Counseling

At each visit, designated study staff or physicians will counsel subjects about the importance of adherence to ART and study medications. Women of child-bearing potential will be counseled about the importance of adherence to contraceptives. There are no potential risks associated with this.

7.1.4 Venipuncture

Venipuncture will be performed at each visit and will be done only in the MCRU or Positive Care Center. Only trained research clinic staff or physicians will be allowed to perform venipuncture. The risks of venipuncture are transient pain, bleeding, lightheadedness, bruising, possible vasovagal reaction, and infection.

7.1.5 Gardasil Vaccination

Gardasil vaccine will be administered to HIV infected subjects at months 23, 25 and 29.5. Only study staff well trained in vaccine administration will be allowed to administer Gardasil. The vaccine will be administered intramuscularly in the thigh at the month 29.5 visit so that local response to the vaccine in the draining inguinal lymph node can be assessed. The most common side effects of this vaccination are headache, fever, nausea, dizziness and injection site reactions. Severe reactions, including hypersensitivity, are rare.

7.1.6 Inguinal Lymph Node Biopsy

Inguinal lymph node biopsies will be performed by [name] or [name], members of the Department of Surgery at the University of Minnesota. HIV infected subjects will have

biopsies performed at baseline and months 12 and 30. HIV uninfected control subjects will have biopsies performed at one time point only. Procedures will be done in the MCRU under local anesthesia. The surgeon will first clean and sterilize the inguinal area, inject a local anesthetic and make a small (5 cm) incision over the lymph node. It will be removed and the incision closed. This technique has been successfully used in over 200 lymph node biopsies at the University of Minnesota in the past 5 years without any significant complications.

The risks of the lymph node biopsy are bleeding, infection, seroma, and scarring. Any participant who develops a seroma will have it drained with a syringe in the clinic. These complications are rare. All post-operative and post-biopsy care will be provided by designated study staff. If complications occur, the subject will be seen immediately by the appropriate study physician(s).

7.1.7 Colonoscopy with Ileal and Rectal Biopsies

Colonoscopies with ileal biopsies will be completed by [name], a member of the Division of Gastroenterology in the Department of Medicine at the University of Minnesota. HIV infected subjects will have biopsies performed at baseline and months 12 and 30. Procedures will be done in the UMMC Endoscopy Center under conscious sedation. Subjects will complete the required bowel regimen the night prior to their scheduled procedure. For the procedure, the participant will lie on their left side and the colonoscope will be inserted and guided through the colon. After 20 small tissue biopsies of the ileum and rectum are obtained, the colonoscope will be removed.

The risks of colonoscopy are abdominal cramping, bleeding, anxiety, and dizziness from the sedation. A very rare complication of colonoscopy is perforation of the intestine. All post-procedure and post-biopsy care will be given by designated study staff who are specially trained to do this.

7.1.8 MRI

MRI will be performed by [name], a faculty member of the Department of Radiology at the University of Minnesota. MRI sub-study participants will undergo MRI one to three weeks prior to the baseline, Month 12 or Month 30 visit. MRI will be performed at the Center for Magnetic Resonance Research (CMRR) without use of contrast dye. Sub-study participants will be screened and consented prior to undergoing MRI by trained CMRR staff. Subjects will be asked to avoid eating or drinking anything for four hours prior to the procedure. The subject will be positioned on their back on the scanner table, will enter the magnet tunnel feet first, and will have a surface coil consisting of a flexible plastic sheet placed around their body and secured with Velcro. A series of scans that in total will last between 60 – 180 minutes will be performed. These scans are intended to develop new methods for acquiring and analyzing MRI data to characterize structural and functional changes of the lymphatic tissue between the normal and disease state.

Risks of moving in/near the scanner and during the MR scanning include dizziness, warming, and muscle twitching. Some metallic objects are attracted to the magnet and cannot be brought into the room. Some participants may experience claustrophobia. The MR scanner makes loud noises. Some people report mild nausea, headache, a metallic taste in their mouth, or sensations of flashing lights that if present, subside shortly after leaving the magnet. There is a risk of unknown effects related to participation in MRI research. There are no benefits to participation. Incidental findings are not expected, but if found, a Radiologist associated with CMRR will review the MR images and will recommend the subject follow-up with their primary medical provider as needed.

See Appendix I for additional information about MRI

7.2 Plan to Minimize Risks to Subjects

All investigators and study staff have completed required training regarding human subject protections. Study staff will comply with all related regulations and laws, included, but not limited to 45 CFR 46 and 21 CFR 50, 56 (FDA version), and HIPAA Privacy Regulations. Study will be conducted in accordance with US and international standards for good clinical practices, applicable regulations, and institutional research policies and procedures.

Subjects will be rigorously screened against inclusion/exclusion criteria to ensure that their participation is safe. All staff members responsible for taking a medical history that could potentially make the participant uncomfortable have been specifically trained for how to do this in a sensitive manner. Only qualified study or clinic staff or physicians will draw blood to minimize risks. Pregnancy testing will be performed at screening, baseline, every 3 months, and anytime during follow up when the woman or investigator suspects pregnancy. In addition, study staff will stress the importance of adherence to contraceptives in order to minimize risks related to unintended fetal exposure. Subjects will be closely observed for systemic adverse events and toxicity related to the study drug on a routine basis through interviews, clinical assessment (including measuring vital signs and physical exam), and monitoring of renal function, liver function, and hematologic panel. All lymph node biopsies will be performed by either [name], [name], or [name] who have performed >400 LN biopsies in the research setting without significant complications. All colonoscopies will be performed by [name] who has performed >300 colonoscopies and biopsies in related HIV studies in the past without any complications. Subjects will be monitored after biopsy procedures for at least 4 hours by study staff trained in managing postoperative patients. They will be monitored for at least 30 minutes after HPV vaccine administration to ensure that they tolerate the vaccine without difficulty.

Samples obtained for pharmacokinetic analysis will be immediately sent to [name] laboratory and will be analyzed in semi real-time. Levels of losartan and all ARVs that an individual subject is taking will be monitored to ensure that subjects are not exposed to supratherapeutic levels of any drug, that losartan does not decrease levels of any ARVs, and that the active metabolite of losartan is within the expected range. Results of these analyses will be communicated to the PI as soon as they are available. If losartan is found to either increase or decrease levels of a particular ARV, the IRB will be notified and all enrolled subjects taking that ARV will be contacted and the finding explained. Depending on the type of drug-drug interaction, toxicity labs and/or HIV VL will be obtained within 3 days of obtaining the drug level results. If dose adjustments can be used to overcome these interactions, they will be made if the subject is willing. If dose adjustments are not possible, subjects taking the ARV will be withdrawn from the study and the protocol will be amended so that no additional subjects taking that ARV will be enrolled. If losartan metabolite levels are found to be lower than the expected range, the losartan dose will be increased. If losartan metabolite levels are higher than expected, toxicity labs will be obtained and the dose will be decreased. After any dose adjustments of losartan or ARVs, follow up drug levels will be monitored closely to ensure that target levels have been achieved.

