4.2.2 Secondary Endpoints

There are 4 secondary endpoints:

1. We will assess the impact of losartan on immune reconstitution and T-cell function by measuring:

- ⇒ Frequency of CD4+ T cells, TUNEL+CD3+CD8+ T cells and cells expressing TGF-beta and lymphotxin-beta in LT using IHC.
- ⇒ Serum levels of IL-7 and TGF-beta using ELISA.
- ⇒ The immune response to HPV vaccination using flow cytometry to identify cells stimulated by specific HPV peptides.

2. We will determine the impact of losartan on immune activation in HIV infected, treated individuals by determining:

- ⇒ Frequency of activated T-cell populations (specifically CD3+CD4+CD38+, CD3+,CD8+CD38+, CD4+Ki67+ and CD8+Ki67+ T cells) in LT using immunofluorescence staining.
- ⇒ Percentage of activated T cells, macrophages and dendritic cells in PBMCs and LT using flow cytometry.
- ⇒ Intracellular levels of the inflammatory cytokines IL-17, IFNg, IL-2, TNF, IL-10, and GM-CSF in PBMCs and LT using cytokine staining.
- ⇒ Plasma levels of additional inflammatory markers including LPS, sCD14, I-FABP, IL-1b, IL-1RA, IL-6, TNF, amyloid A, CRP, and D-dimer using limulus assay (sCD14) and ELISA (all others).

3. We will assess the potential for losartan to reduce the size of the viral reservoir by determining the frequency of HIV RNA+ and DNA+ cells in LN and GALT using both radiolabeled in situ hybridization (ISH) and RNAscope™ in situ technology.

4. To ensure that losartan is safe and well tolerated when used with ART, we will:

- ⇒ Perform an intensive pharmacokinetics experiment in all HIV infected subjects at month 1 of the study (when losartan is at steady state).
- ⇒ Measure levels of ARTs and losartan in plasma and PBMCs quarterly over the 30-month study period.
- ⇒ Measure intracellular levels of losartan and ARTs in LT at month 30.

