8.1.4 Month 1 Visit

Subjects will be seen at month 1 for clinical assessment (interval history and targeted exam) and review of drug adherence. Blood will be drawn. They will then take their daily ART and study drug and will remain in the MCRU for additional blood draws at 1, 2, 3, 4, 6, 8, and 12 hours after drug administration in order to intensively study the pharmacokinetics of ARTs and losartan. They will then return to the MCRU the following morning for one additional blood draw at 24 hours after drug administration.

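### Section 7.2 reports losartan and metabolite levels to the PI during treatment, which would show the PI the arm that 9.8 and 11.3 keep blinded

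*Combined protocol and SAP*

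**What the plan says.** Section 7.2 describes monitoring of losartan, its active metabolite and every antiretroviral that a subject takes, with assays run close to real time. On reporting it says: "Results of these analyses will be communicated to the PI as soon as they are available". Two dosing rules follow: "If losartan metabolite levels are found to be lower than the expected range, the losartan dose will be increased" and "If losartan metabolite levels are higher than expected, toxicity labs will be obtained and the dose will be decreased". For an interaction with an antiretroviral (ARV), "all enrolled subjects taking that ARV will be contacted and the finding explained", and "toxicity labs and/or HIV VL will be obtained within 3 days of obtaining the drug level results".

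The sampling covers both arms. Section 4.2.2 plans to "Perform an intensive pharmacokinetics experiment in all HIV infected subjects at month 1 of the study". Section 8.1.4 has the month 1 dose taken on site: "They will then take their daily ART and study drug and will remain in the MCRU for additional blood draws". Table 1 adds further losartan levels about every quarter.

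On blinding, section 9.8 places participants, investigators, study staff, the statistician and the DSMB under the blind. Section 11.3 exempts only the IDS pharmacy, and holds the blind until the data have been entered and verified and are ready for the final analysis.

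**The concern.** In a placebo-controlled trial, a measured level of the active drug amounts to a statement of the arm. Section 7.2 sends that measurement to the PI while treatment continues, and the PI is one of the people whom 9.8 and 11.3 keep blinded. Following 7.2 would therefore break the other two sections.

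The PI also rates how each adverse event relates to the study drug (9.3.2). That rating feeds dose reduction, stopping and re-challenge (8.1.3), discontinuation for toxicity above grade 2 (9.6) and removal from the study (9.7.2). A PI who knows the arm may attribute the same event differently in the two arms, and a blind that has been lost cannot be restored later.

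**Working it through.** The plan gives no figure to reproduce here. The check compares sections and counts visits.

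1. **Who is measured, and how often.** All HIV infected subjects have intensive PK at month 1 (4.2.2). Table 1 marks losartan levels at months 1, 3, 6, 9, 12, 15, 18, 21, 25, 27 and 30, which is 11 visits. Four (months 1, 3, 6 and 9) come before the month 12 biopsies, and 10 come before the month 30 visit.

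2. **How clear one result is.** Section 8.1.4 has one blood draw before the dose, then "blood draws at 1, 2, 3, 4, 6, 8, and 12 hours after drug administration", then one at 24 hours. That is 1 + 7 + 1 = 9 samples, 8 of them after a dose taken on site. Missed doses at home are therefore unlikely to hide losartan in a treated subject, and a placebo subject should have none.

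3. **Whether another reading of 7.2 protects the blind.**
   - If losartan is assayed only in treated subjects, the existence of a result shows the arm, and the laboratory would need the codes.
   - If the PI receives only group summaries, the rules that change one subject's dose cannot be applied from them.
   - If the PI receives only dose instructions, 7.2 does not say so.
   - The low-level rule fails under blinding in any case. An undetectable metabolite in a placebo subject would call for a dose increase, and limiting the rule to losartan subjects requires the code.

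4. **Whether an unblinding route covers it.** Section 9.8.2 concerns an SAE where treatment planning needs the code. Section 9.8.3 concerns an analysis that the DSMB requires. Section 9.8.4 concerns the end of the study. None of these provides for PK results. Section 9.8.1 only points to a pharmacy SOP that is not among the documents.

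5. **How many subjects.** The plan enrols 63 so that 50 complete: 50 / (1 − 0.20) = 62.5, rounded up to 63. Section 9.7.2 replaces subjects withdrawn before month 1, so every completer has the month 1 visit behind them. The number exposed is at least the 50 planned completers and at most 63. The documents do not show that all 63 reach month 1.

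6. **How long.** For a subject who stays 30 months, the share of treatment after the month 1 result is (30 − 1 − t) / 30, where t is the reporting delay in months. The delay is not stated, so I assume 0 to 3 months: 29/30 = 96.7% at t = 0, and 26/30 = 86.7% at t = 3. Subjects who leave early have less exposed time; past drop-out was 20 to 25% (section 2.2). These figures describe exposure of the blind, not the size of a bias.

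**The case against.** The strongest reply is that little of what the trial formally tests depends on the PI's judgement. The primary endpoint is collagen and network integrity by immunohistochemistry and image analysis (4.2.1). Secondary endpoints 1 to 3 are laboratory assays. Secondary endpoint 4 opens with safety and tolerability, but the measures listed under it are drug levels, not adverse event ratings. Severity grading uses a fixed table (9.3.1), and the first three escalation criteria in 8.1.3 are numeric. Much of the discretion over dose in 8.1.3 belongs to the site investigator, whereas 7.2 names only the PI as recipient. All of this stands, and it limits how serious the point is. It does not remove the conflict: the relatedness rating is the PI's, and stopping and removal follow from it.

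The second reply is about certainty. Section 7.2 does not give the form of the report, so subject-level reporting is an inference, though a strong one. The 9.8.1 pharmacy SOP, Manual of Procedures, Data Management Plan and Specimen Management Plan were not available and might contain a masking step. Section 7.2 refers to none.

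A reader might also take the monthly laboratory reports that 14.3 files in study charts as a second leak. The laboratory names are removed from the text, so it cannot be read whether the PK laboratory is among them, and the point does not rest on that section.

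**Conclusion.** The conflict between 7.2 and the blinding rules in 9.8 and 11.3 is real and should be fixed. On the natural reading, the PI can tell the arm of nearly every subject once the month 1 result is reported. This assumes that results are reported by subject and that no document outside the supplied set masks them.

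The damage shown is limited to the PI's relatedness ratings and the stopping and removal decisions that follow. A reader might infer that the collagen result is biased too, for example through arm-dependent loss of biopsies. The documents do not support that: the PI does not score the endpoint, 8.1.3 allows re-challenge at a lower dose, and 9.7.2 lets a participant stop the drug and stay in follow-up. The documents give no event or withdrawal rates by arm, so the size of any bias cannot be stated. The point is worth an amendment but does not put the primary analysis in question.

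**What to change.** - **Section 7.2, reporting.** Send losartan and metabolite results only to the IDS pharmacy, which already holds the codes. Send the PI ARV levels only, without delay, so that the PI can act on an out-of-range ARV in either arm.
- **Section 11.3.** List the PK laboratory as not blinded to losartan results.
- **High metabolite level.** Keep the action in 7.2. The pharmacy prompts the toxicity labs and makes the dose decrease through blinded supply.
- **Low metabolite level.** Any increase stays within the 100 mg limit in 8.1.3 and needs the blinded site investigator's agreement. That means criteria a to f and, after an earlier dose reduction, the discretion that 8.1.3 gives the site investigator. The pharmacy should not raise a dose alone.
- **Confirmed interaction.** Tell the PI which ARV is affected, not subjects' losartan levels. The contact in 7.2 already goes to everyone taking that ARV, so it does not reveal the arm. The 3-day limit for labs after the drug-level result stays, and the referral must fit inside it.
- **Optional.** Sham dose changes or lab requests in placebo subjects would hide the meaning of an action further.

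The protocol already works this way once: in 11.3 the pharmacist picks the two-photon participants because investigators are blinded. The cost is an amendment to 7.2 and 11.3 and some referral work for the laboratory and pharmacy. A small chance remains that a dose action hints at the arm.

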8.1.3 Day 14 Visit

Subjects will be seen at day 14 for clinical assessment (interval history and targeted exam), assessment of drug adherence and to obtain toxicity labs (CBC and CMP). If the subject meets the following criteria: lack of dizziness, lightheadedness, or faintness upon rising, confusion, palpitations, and cough; GFR greater than or equal to 30 mL/min/1.73 m² and potassium level less than or equal to 5.0, the dose of losartan/placebo will be increased to 100 mg po daily. The maximal tolerable dosage (up to 100 mg a day) will be continued for a total of 30 months.

At Day 14, side effects and blood chemistries (comprehensive chemistry panel) will be assessed. The dose of losartan/placebo will increase to 100mg daily at this Day 14 visit (i.e., once lab results return) if all of the following criteria are met:

- a) Systolic blood pressure (BP) ≥ 90 mmHg
- b) Potassium ≤ 5.0 mmol/L
- c) eGFR ≥ 30 mL/min/1.73m²

- d) Lack of a grade ≥ 3 side effect since the last evaluation deemed possibly/probably related to the study drug.
- e) Lack of significant side effects deemed related to study drug (e.g., lightheaded upon standing)
- f) Lack of other concerns to increase study drug dosing, as determined by site investigator

Participants may be evaluated by clinical labs and/or have side effects assessed at any point during the study, per the discretion of the site investigator. If participants are increased to 100mg daily (or matching placebo) they will maintain this dose for the duration of the 30-month study unless new side effects or adverse events necessitate re-evaluation (see below criteria for dose reduction or stopping study medication).

If participants do not increase dose to 100mg daily at the week 2 visit (e.g., if symptomatic or if systolic BP is not ≥ 90 mmHg), the criteria for dose escalation may be reassessed at the 1-month visit. If participants do not meet criteria for dose increase (from 50mg to 100mg daily) after the 1-month visit, they will be maintained on 50mg dose until the month 3 visit, at which time the dose may be increased to 100mg daily if the first five criteria above are met (a-e). At any point when participants have dose increased from 50mg to 100mg, they will be contacted by phone within 2 weeks to assess side effects and have clinical labs drawn to assess toxicity; a full study visit for side effect and adverse event documentation can occur at any point, per the discretion of the site investigator.

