Dose Reduction: Tolerability, side effects, and clinical laboratory monitoring will be assessed at each study visit (via participant report and clinical labs), and at any other time point at the discretion of the clinical site investigator. Adverse events that are assessed as related to study drug will prompt re-evaluation via phone or as an adverse event visit, per clinical discretion of the site investigator. If this event worsens or does not resolve after re-evaluation, then study medication dose should be decreased (i.e., from 100mg to 50mg) or stopped (if taking 50mg daily). If signs and symptoms resolve after 2 weeks, then the participant may resume or increase dose (i.e., back to 100mg if previously reduced to 50mg daily), per the clinical discretion of the site investigator.

Stopping Study Medication: If an adverse event of grade ≥ 3 is assessed as related to study drug, study medication should be stopped and the participant should be re-evaluated in 2 weeks. If a grade 2 rash is persistent, study medication may also be stopped at the discretion of the site investigator and the participant should be re-evaluated in 2 weeks. If signs and symptoms resolve after 2 weeks, then the participant may be re-challenged at a lower dose (i.e., at 50mg if previously taking 100mg daily) per the clinical discretion of the site investigator. If study medication is stopped for an adverse event that is later determined NOT to be related to study medication, then the medication may be resumed at 50mg and increased to 100mg per initial criteria for dose escalation and at the discretion of the clinical site investigator.

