8.2 Schedule of Events for HIV Infected Subjects

Table 1. Protocol summary for HIV infected subjects:

	Screen	Day 0	Day 14	Month 1	Months 3, 6, 9, 15, 18, 21, 27	Month 12	Month 23	Month 25	Month 29.5	Month 30
Medical history	X	X								
Interval medical history			X	X	X	X	X	X	X	X
Physical Exam ¹	X	X	X	X	X	X	X	X	X	X
Adherence assessment and counseling		X	X	X	X	X	X	X	X	X
Pregnancy test ²	X	X		X	X	X		X	X	
HCV Ab	X									
CMP	X	X	X	X	X	X	X		X	X
CBC w diff	X	X	X	X	X	X	X		X	X
CD4 count	X	X		X	X	X	X		X	X
HIV viral load	X	X		X	X	X	X		X	X
Serum ³		X		X	X	X	X	X	X	X
Plasma /PBMCs ⁴		X		X	X	X	X	X	X	X
Additional PBMCs ⁵		X				X				X
Biopsies ⁶		X				X				X
HPV vaccine ⁷							X	X	X	
PK assessment				X ⁸	X ⁹	X ⁹		X ⁹		X ¹⁰

1. At screening, a full physical exam will be performed (described above). At subsequent visits, a targeted exam will be performed.
2. Women of childbearing age must have a negative pregnancy test prior to enrollment. Pregnancy testing will also occur roughly every 3 months during follow up and additionally if the subject or investigator suspects pregnancy.
3. Serum will be used to determine levels of IL-7 and TGF-beta.
4. Plasma will be used to determine levels of cytokines and markers of inflammation. PBMCs will be used in flow cytometry and intracellular cytokine staining.
5. Additional blood will be obtained from subjects enrolled in the two-photon microscopy sub-study.
6. Inguinal LN biopsy and colonoscopy with sampling of ileal and rectal tissues.
7. Human papillomavirus quadrivalent vaccine (Gardasil) will be administered at 3 time points per recommended vaccine schedule and immune response will be assessed at month 30.
8. Intensive 24-hour PK assessment will be performed at month 1 visit.
9. Plasma and intracellular PBMC concentration of losartan and ARVs will be determined approximately every quarter.
10. Plasma and intracellular PBMC concentration of losartan and ARVs PLUS concentrations in LN and GALT will be determined at month 30.

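### Section 7.2 orders a losartan increase for any low metabolite level, against the 100 mg cap and the 50 mg holds in section 8.1.3

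*Combined protocol and SAP*

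**What the plan says.** Section 7.2 (Plan to Minimize Risks to Subjects) covers the response to drug-level results, which are analysed in semi real-time and sent to the investigator. For the losartan metabolite it says: "If losartan metabolite levels are found to be lower than the expected range, the losartan dose will be increased". After any adjustment, "follow up drug levels will be monitored closely to ensure that target levels have been achieved". A high level, by contrast, leads to toxicity labs and a lower dose.

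Section 8.1.3 (Day 14 Visit) sets the dosing rules:

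- **Cap:** "The maximal tolerable dosage (up to 100 mg a day) will be continued for a total of 30 months".
- **Once at 100 mg:** "they will maintain this dose for the duration of the 30-month study unless new side effects or adverse events necessitate re-evaluation".
- **Before going to 100 mg:** systolic pressure of at least 90 mmHg, potassium no higher than 5.0 mmol/L, eGFR of at least 30, and side-effect criteria.
- **If the criteria are still unmet after the month 1 visit:** "they will be maintained on 50mg dose until the month 3 visit, at which time the dose may be increased to 100mg daily", provided criteria a to e are then met.
- **After a drug-related event that worsens or persists:** the dose is halved to 50 mg, or stopped if already 50 mg. A return to the higher dose is allowed if the event has resolved after 2 weeks, at the site investigator's discretion.

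Section 8.1.4 places the intensive sampling day at month 1, "in order to intensively study the pharmacokinetics of ARTs and losartan". A footnote to Table 1 (section 8.2) adds: "Plasma and intracellular PBMC concentration of losartan and ARVs will be determined approximately every quarter".

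**The concern.** The section 7.2 instruction is mandatory and unconditional. The qualifiers near it, on the participant's willingness and on whether adjustment is possible, belong to the sentences on antiretroviral interactions and do not limit it. Section 8.1.3 gives a different instruction for some of the same participants, neither section refers to the other, and no text sets an order of precedence.

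Followed literally, section 7.2 would take a participant above 100 mg, a dose no section supports. The tolerability precedent cited in section 2.2 covers only the 50-to-100 mg scheme. It would also raise the dose in someone held back for low blood pressure, high potassium, low eGFR or a drug-related event. Section 2.4.1 lists symptomatic hypotension, worsening renal function and electrolyte abnormalities among the drug's most severe risks, and these are what the section 8.1.3 criteria screen for. Staff who hold the dose breach section 7.2; staff who raise it breach section 8.1.3.

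**Working it through.** There is no planned figure to reproduce. The check sets the two instructions side by side for each dosing state, and then counts how often the rule can be triggered.

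**Case check, given a low metabolite level**

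| Participant's state | Section 7.2 | Section 8.1.3 | Compatible? |
|---|---|---|---|
| At 100 mg | Increase | Cap of 100 mg; keep unless side effects or adverse events arise | No |
| At 50 mg, criteria unmet after month 1 | Increase | Stay at 50 mg to month 3, then only if a to e are met | No |
| Reduced to 50 mg, event unresolved | Increase | Go up only after resolution, at discretion | No |
| At 50 mg, criteria met or event resolved | Increase | 100 mg allowed | Yes |

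A low level is neither a side effect nor an adverse event, so in the first row it does not reopen the 100 mg dose.

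The second row can arise at once. The intensive sampling day is month 1 and the hold runs from month 1 to month 3, so the first low result can arrive during the hold.

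**Order of safeguards.** For a low level, section 7.2 requires repeat levels after the change and no labs before it. The section 8.1.3 phone contact and labs likewise follow an increase from 50 to 100 mg, and nothing covers a step above 100 mg.

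**Number of occasions** (pharmacokinetic row of Table 1)

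- Month 1: 1
- Months 3, 6, 9, 15, 18, 21 and 27: 7
- Month 12: 1
- Month 25: 1
- Month 30: 1

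Total: 1 + 7 + 1 + 1 + 1 = 11. Remaining study drug is collected at month 30 (section 8.1.10), so 11 − 1 = 10 assessments can still change a dose.

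**The case against.** The strongest reply is that the section 7.2 sentence should not be read alone. It names no dose, and every section that does (Protocol Summary, 2.2, 4.1, 6.1.1.2, 8.1.3) stops at 100 mg. Section 6.1.1.2 also ties the step to 100 mg to tolerability, blood pressure and toxicity labs. On that reading, an increase can only mean 50 to 100 mg.

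Safety information is also at hand. Table 1 schedules a physical exam, which includes vital signs, at all 10 of these visits, and a metabolic panel at 9 of them (all but month 25). Section 6.3 requires a package-insert review whenever a dose changes. Sections 9.6 and 9.7.2 take participants off losartan for related toxicity above grade 2, so the reduced-dose case is mostly unresolved grade 1 or 2 events. The 10 occasions are an upper bound on opportunity: only the month 1 sample falls at the start of the explicit 50 mg hold. The sponsor may also have intended a separate, interaction-driven adjustment.

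Much of this is right as fact. It shows that the rest of the protocol agrees with section 8.1.3 and that the data needed for a safety check will usually exist. It does not make the section 7.2 increase depend on those data or on the cap. Section 8.1.3 grants discretion; the section 7.2 sentence does not. If a separate adjustment was intended, its upper dose and its safety conditions are not stated.

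**Conclusion.** The concern holds. Three of the four dosing states give contradictory instructions on a low level, and no text resolves them. Each losartan participant who completes the schedule has 10 assessments at which the rule could be triggered. That is a count of opportunities, not of expected conflicts: the documents give no expected range for the metabolite, do not say whether it depends on dose, and state no turnaround time for results. The conclusion rests on reading the mandatory wording of section 7.2 as it stands. It touches no endpoint, sample size, power or alpha. It needs correcting because a written dosing rule, if followed, gives an unsafe dose or a protocol violation.

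**What to change.** Amend the sentence in section 7.2 so that section 8.1.3 governs, for example:

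> A low metabolite level may lead to an increase only from 50 mg to 100 mg, and only if the section 8.1.3 escalation criteria are met (or, after a dose reduction, the section 8.1.3 conditions for resuming). For a participant already at 100 mg, or one who does not meet those criteria, a low level leads to an adherence check and a repeat level, with no dose increase.

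The cost is a short amendment with a cross-reference. Pill counts are already taken at each visit (section 6.2), and the repeat level can use samples already in Table 1, so no visits are added. The wait for that sample is between 2 months (month 1 to month 3: 3 − 1) and 4 months (month 21 to month 25: 25 − 21). If the sponsor wants a faster answer, an earlier repeat sample would be a small extra cost. The same amendment could usefully state the expected range.
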